6.3 SUMMARIES OF DEMOGRAPHIC AND BASELINE CHARACTERISTICS

Demographic and baseline characteristics (including age, sex, race and ethnicity, height, weight, medical history, concomitant medication, serology etc) will be summarized using means, *SD*, medians, and ranges for continuous variables and proportions for categorical variables, as appropriate.

The assignment of subjects to subject samples, the disposition of subjects with respect to premature termination, reason for premature termination, drug exposure will be summarized.

Medical history, including coding data will be summarized per primary SOC by PT. Additionally medical history will be listed. Protocol deviations will be listed. Prior/concomitant medications will be summarized per Therapeutic or chemical group and preferred WHO name. Additionally prior/concomitant medications will be listed.

6.4 EFFICACY ANALYSES

The *FAS* set will be used for the efficacy analysis. All efficacy parameters *will be* summarized with descriptive statistics (mean, *SD*, median, minimum maximum, 95% CI) for each measurement time point.

6.4.1 Primary Efficacy Endpoint

The primary outcome variable is the absolute change in FVC from Baseline to Week 26 (both in mL and % predicted). Baseline FVC will be the average of the highest FVC measurement recorded at the Screening and Day 1 visits. The FVC at Week 26 will be the average of the highest FVC measurement recorded on two separate days at Week

Pirfenidone—F. Hoffmann-La Roche Ltd

26. Data will be analyzed using a standard descriptive statistics for continuous variables and 95% CI for the mean.

The data imputation methods for primary endpoint are described in [Section 6.2](#).

The distribution (number and percentage) of primary outcome variable by patients across *three* categories of change from Baseline (Decline of $\geq 10\%$ or death before Week 26; *Decline of $< 10\%$ to 0%* ; Improvement of $\geq 0\%$) will be provided in frequency table.

Additionally, the absolute change in FVC from Baseline at Week 12, 39 (optional) and 52 (optional) and mean FVC change through all time endpoints (both in mL and % predicted) will be summarized in tables with standard descriptive statistics for continuous variables and 95% CI for mean.

6.4.2 Secondary Efficacy Endpoints

Change in 6MWT distance from Baseline to Week 26

Baseline 6MWT distance will be the average of the measurements recorded at the Screening and Day 1 visits. The 6MWT distance at Week 26 will be defined as the average of the 6MWT distance recorded on two separate days at Week 26. Data will be analyzed using a standard descriptive statistics for continuous variables and 95% CI for mean.

The distribution (number and percentage) of 6MWT distance by patients across two categories of change from Baseline (Decline of ≥ 50 m or death before Week 26; Improvement of ≥ 0 m) will be provided in frequency table.

Additionally, the absolute change in 6MWT from Baseline at Week 39 (optional) and Week 52 (optional) will be summarized in table with standard descriptive statistics for continuous variables and 95% CI for mean.

Change from Baseline to Week 26 in patients' quality of life as measured with EQ-5D-5L

Results of EQ-5D-5L questionnaire will be summarized in two ways:

- Cross tabulation for each of five dimensions (Mobility, Self-Care, Usual Activities, Pain / Discomfort, Anxiety / Depression) by response and study week.
- VAS score, including changes from baseline, will be summarized with descriptive statistics (mean, standard deviation, median, minimum and maximum) for study week.

Pirfenidone—F. Hoffmann-La Roche Ltd

138/Protocol ML39355, Version 2 dated 09-Jun-2018

Additionally, a single *Index* score will be provided, if necessary.

6.4.3 Exploratory Efficacy Endpoints

HRCT fibrosis score

The HRCT findings will be evaluated using HRCT scoring system. One ILD radiologist will make assessments of 4 main findings in three zones of each lung. The six zone scores will be averaged to determine the total score for each patient. Score will be recorded at the initial diagnosis and after six and 12 months in a similar manner for further comparison. The mean \pm SD of HRCT fibrosis score like continuous variable will be determined obligatory at baseline, 6 *months* and optional at 12 months.

The values of HRCT fibrosis score at baseline, at Week 26 (optional) and Week 52 (optional) will be summarized in table with standard descriptive statistics for continuous variables and 95% CI for the mean.

Additionally, the absolute change of HRCT fibrosis score from baseline at Week 26 (optional) and Week 52 (optional) will be summarized in table with standard descriptive statistics for continuous variables and 95% CI for the mean.

The paired t-test will be performed to evaluate the changes in the variable from the baseline to Week 26 (optional) and Week 52 (optional), respectively. The type I error rate will be set to 5%.

Lung opacity (ground-glass attenuation)

The sign 'lung opacity' will be qualified separately using methodology described above for other signs, and its change over time will be assessed outside the framework of a total summed index of fibrosis (HRCT fibrosis score). Lung opacity should be graded as reticular abnormality to calculate the score for each zone, i.e. the percentage (%) area of opacity in a zone should be multiplied by the score of 2.

The percentage area of opacity at Baseline, at Week 26 (optional) and Week 52 (optional) will be summarized in table with standard descriptive statistics for continuous variables and 95% CI for *the* mean.

Additionally, the absolute change of percentage area of opacity from Baseline at Week 26 (optional) and Week 52 (optional) will be summarized in table with standard descriptive statistics for continuous variables and 95% CI for *the* mean.

Exacerbations

Pirfenidone—F. Hoffmann-La Roche Ltd

An exacerbation will be defined as an AE with special criteria, *i.e. only in case the exacerbation has led to death of a patient* (see [Section 5.2.1](#)). Rate of exacerbation will be reported in three following tables:

- Exacerbation cases during treatment period (until Week 26).
- Exacerbation cases during long-term follow-up period (from Week 26 to Week 52).
- Exacerbation cases during whole study period (from Day 1 to Week 52, applicable only for subjects continuing in the rollover study).

Exacerbation cases will be listed.

6.5 SAFETY ANALYSES

The *Treated set* will be used for the analysis of the safety and tolerability data.

Study treatment is defined as pirfenidone 2403 mg/d administered in divided doses TID with food. Study treatment will be titrated over 14 days to the full dose of 9 capsules per day (three 267-mg capsules taken orally TID with food). Patients will remain on a stable maintenance dose for the duration of the treatment period unless the dose is reduced to manage an AE or titrated again when restarting study treatment after a 28-day or greater interruption in treatment.

AEs will be reported on a per-subject basis, *i.e.* counting subjects rather than events. Only treatment emergent AEs will be reported. In the listings, however, all occurrences of the AEs will be presented.

Treatment emergent AEs will be summarized per primary *SOC* and *PT*. Severity and drug-event relationship of treatment emergent AEs will be summarized separately.

Vital signs, including changes from baseline will be listed *and* summarized with descriptive statistics (mean, *SD*, median, minimum and maximum) for each measurement time point. Out-of-range values with assessment of clinical significance will be provided in frequency tables.

Results of ECG, including changes from baseline will be listed *and* summarized with descriptive statistics (mean, *SD*, median, minimum and maximum) for each measurement time point. Out-of-range values with assessment of clinical significance will be provided in frequency tables.

Pirfenidone—F. Hoffmann-La Roche Ltd

140/Protocol ML39355, Version 2 dated 09-Jun-2018

Laboratory variables, including changes from baseline will be listed and summarized with descriptive statistics (mean, *SD*, median, minimum and maximum) for each measurement time point. Additionally, shift tables summarizing the frequencies of patients below, within, and above the normal ranges at each time point will be provided.

Results of physical examinations will be summarized in corresponding frequency table and listing.

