Treatment with pirfenidone will continue until Week 26 (± 1). Patients will be followed through the Follow-up visit scheduled 2-4 weeks after treatment completion or until entry into the long-term follow-up (rollover study), whichever occurs earlier. Patients who undergo lung transplantation or who chose to withdraw from study procedures early will be followed for vital status until Week 26. If patients discontinue study treatment early for any reason, they should continue with all scheduled study procedures through Week 26.

Patients who complete participation in the study prematurely due to any reasons (drop-outs) will not be replaced.

[figure not shown]
Patients who proceed until Week 26 in the study and are compliant with the study treatment, may continue treatment with commercially available pirfenidone after study completion in real clinical practice (long-term follow-up or rollover study). In this case, patients will have two follow-up assessments of FVC and 6MWT at Weeks 39 and 52 and CT scans evaluation at Week 52. Information on AEs occurrence will also be collected during the rollover part of the study.

If a patient cannot participate in the rollover part of the study for any reason, a follow-up visit will be performed 14-28 days after the last dose of pirfenidone is taken.

Pirfenidone—F. Hoffmann-La Roche Ltd

The study schema is presented in [Figure 1](#) below. A schedule of activities is provided in [Appendix 1](#).

Figure 1 Study Schema

An Independent Data Monitoring Committee (IDMC) will be implemented in the study. The IDMC will conduct regular review of the trial safety data, with the focus on death cases, serious adverse events, unexpected adverse events, adverse events leading to treatment or study discontinuation, liver enzyme increases, reported as adverse events, and other AEs immediately reported to the Sponsor (see [Section 5.2.3.2](#)).

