4.5.8 Laboratory, Biomarker, and Other Biological Samples

All samples for laboratory tests (hematology, blood chemistry, serologic tests) will be analyzed in the study site's local laboratory.

Blood samples should be obtained in fasted patients and handled appropriately. The following parameters will be utilized in the study:

- hematology (plasma): white blood cells (WBC) count, red blood cells (RBC) count, hemoglobin, hematocrit, platelet count, (relative) differential WBC count (neutrophils, eosinophils, basophils, monocytes, lymphocytes);
- blood chemistry panel (serum or plasma): albumin, alkaline phosphatase (AP), ALT, AST, direct bilirubin, total bilirubin, total protein, albumin, cholesterol, creatine kinase (CK), creatinine, triglycerides, gamma-glutamyl transferase

Pirfenidone—F. Hoffmann-La Roche Ltd

(GGT), glucose, lactic dehydrogenase (LDH), calcium, phosphorus, magnesium, potassium, sodium, urea nitrogen, uric acid;

- serologic tests (at screening only, exclusion tests): rheumatoid factor, anticyclic citrullinated peptide and antinuclear antibody titer.

Creatinine clearance

Creatinine clearance should be assessed at the Screening for eligibility confirmation using the following formula by Cockcroft-Gault (Cockcroft DW et al, 1976):

For serum creatinine concentration in mg/dL:

$$\text{CrCl (mL/min)} = (140 - \text{age (years)}) \times \text{weight (kg)} \times 1.0 / 72 \times \text{serum creatinine (mg/dL)}$$

For serum creatinine concentration in $\mu\text{mol/L}$:

$$\text{CrCl (mL/min)} = (140 - \text{age (years)}) \times \text{weight (kg)} \times 1.0 / 0.81 \times \text{serum creatinine (\mu mol/L)}$$

Pregnancy test

All women of childbearing potential will have a urine pregnancy test at the Screening and on Day 1 before start of treatment. Only women with negative pregnancy test will be included in the study. Urine pregnancy tests will be performed repeatedly at specified subsequent visits as scheduled in the [Appendix 1](#).

If a urine pregnancy test is positive, it must be confirmed by a serum pregnancy test. Women with confirmed positive pregnancy test should be immediately withdrawn from the study treatment (see [Section 5.4.3](#)). Urine pregnancy test will be performed by the investigator using test-strips with least sensitivity to human chorionic gonadotropin (hCG) of 10 mLU/mL.

The investigator can perform clinical laboratory assessments more frequently, if it is clinically indicated.

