4.5.9 Electrocardiograms

Single ECG recordings will be obtained at specified timepoints, as outlined in the schedule of activities (see [Appendix 1](#)), and may be obtained at unscheduled timepoints as indicated.

All ECG recordings must be performed using a standard high-quality, high-fidelity digital electrocardiograph machine equipped with computer-based interval measurements. Lead placement should be as consistent as possible. ECG recordings must be performed after the patient has been resting in a supine position for at least 10 minutes. All ECGs are to be obtained prior to other procedures scheduled at that same time (e.g., vital sign measurements, blood draws, *bronchodilator test*) and should not be obtained within 3 hours after any meal. Circumstances that may induce changes in heart rate, including environmental distractions (e.g., television, radio, conversation) should be avoided during the pre-ECG resting period and during ECG recording.

For safety monitoring purposes, the investigator must review, sign, and date all ECG tracings. Paper and digital copies of ECG tracings will be kept as part of the patient's permanent study file at the site. The following should be recorded in the appropriate eCRF: heart rate, RR interval, QRS interval, PR duration, uncorrected QT interval, and QT interval corrected for heart rate using Fridericia's method (QTcF) based on the machine readings of the individual ECG tracings. Any morphologic waveform changes or other ECG abnormalities must be documented on the eCRF. If considered appropriate by the Sponsor, ECGs may be analyzed retrospectively at a central laboratory.

If at a particular postdose timepoint the QTcF is > 500 ms and/ or > 60 ms longer than the baseline value, another ECG must be recorded, ideally within the next 5 minutes or in the utmost 24 hours, and ECG monitoring should continue until QTcF has stabilized on two successive ECGs. The Medical Monitor should be notified. Standard-of-care treatment may be instituted per the discretion of the investigator. A decision on study drug discontinuation should be made, as described in [Section 5.1.2](#). The investigator should also evaluate the patient for potential concurrent risk factors (e.g., electrolyte abnormalities, co-medications known to prolong the QT interval, severe bradycardia).

4.5.10 6-Minute Walk Test

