4.5.13.6 Weeks 12 (\pm 2 Days)

The following procedures will be performed at Week 12:

- Directed history (including review of AEs/SAEs, concomitant medications, oxygen use, hospitalizations, dosing)
- EQ5D questionnaire (should be performed before any other non-PRO assessments)

Pirfenidone—F. Hoffmann-La Roche Ltd

- Physical examination, vital signs, and weight
- Clinical laboratory assessments, including hematology, serum chemistries, and pregnancy test for women of childbearing capacity
- Spirometry (FVC)
- 6MWT and Borg Scale
- Review patient's diary

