9.4. Clinical Laboratory Evaluations

eCRF form: “HEMATOLOGY”, “SERUM CHEMISTRY”.

Clinical laboratory evaluations as scheduled in the Table 1 include the following parameters:

- hematology (plasma): white blood cells (WBC) count, red blood cells (RBC) count, hemoglobin, hematocrit, platelet count, (relative) differential WBC count (neutrophils, eosinophils, basophils, monocytes, lymphocytes);
- blood chemistry panel (serum or plasma): albumin, alkaline phosphatase (AP), ALT, AST, direct bilirubin, total bilirubin, total protein, cholesterol, creatine kinase (CK), creatinine, triglycerides, gamma-glutamyl transferase (GGT), glucose, lactic dehydrogenase (LDH), calcium, phosphorus, magnesium, potassium, sodium, urea nitrogen, uric acid;

Creatinine clearance should be assessed at the Screening for eligibility confirmation using the following formula by Cockcroft-Gault (Cockcroft DW et al, 1976):

For serum creatinine concentration in mg/dL:

ML39355_STATISTICAL ANALYSIS PLAN_Final 2.0_17 June 2020

$$\text{CrCl (mL/min)} = (140 - \text{age (years)}) \times \text{weight (kg)} \times 1.0 / 72 \times \text{serum creatinine (mg/dL)}$$

For serum creatinine concentration in $\mu\text{mol/L}$:

$$\text{CrCl (mL/min)} = (140 - \text{age (years)}) \times \text{weight (kg)} \times 1.0 / 0.81 \times \text{serum creatinine } (\mu\text{mol/L})$$

For laboratory parameters the following tables will be presented according to section 7:

- descriptive statistics of measured values and changes from baseline (including creatinine clearance);
- shift tables based on comparison with normal range (Lower/Normal/Higher);
- frequency tables for Out of range: No/Yes clinically significant (Yes CS) / Yes non-clinically significant (Yes NCS) for laboratory parameters.

All laboratory data will be listed.

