Data extracted: DD.MM.YYYY

ML39355_STATISTICAL ANALYSIS PLAN_Final 2.0_17 June 2020
Pregnancies

F. Hoffmann-La Roche Ltd
 ML39355
Table 3.15 Urine pregnancy test
 Treated set (TS)
 Page X of X

	Total (N = XX) n (%)
Screening	
n'	XX
Done [1]	XX (XX.X)
Negative [2]	XX (XX.X)
Positive [2]	XX (XX.X)
Not Done [1]	XX (XX.X)
Male subject [1]	XX (XX.X)
Female subject with no childbearing potential [1]	XX (XX.X)
Other [1]	XX (XX.X)
Day 1	
n'	XX
Done [1]	XX (XX.X)
Negative [2]	XX (XX.X)
Positive [2]	XX (XX.X)
Not Done [1]	XX (XX.X)
Male subject [1]	XX (XX.X)
Female subject with no childbearing potential [1]	XX (XX.X)
Other [1]	XX (XX.X)
...	
...	...

N: the number of women of childbearing potential in the TS. n' - the number of valid observations.

n: the number of patients within a specific category.

[1] Percentages are based on the corresponding number of valid observations.

[2] Percentages are based on the number of patients for whom the pregnancy test was performed.

Path to the program code, date and time of output

Data extracted: DD.MM.YYYY

<The following Urine pregnancy test assessments will be presented: Screening, Day 1, Week 4, Week 8, Week 12, Week 20, Week 26 Day 2>

ML39355_STATISTICAL ANALYSIS PLAN_Final 2.0_17 June 2020
Laboratory tests

 F. Hoffmann-La Roche Ltd
 ML39355

Table 3.16 Hematology. Descriptive statistics

Treated set (TS)

Page X of X

Parameter: XXXXXXXXXXXXXXXXXXXX, <units>

	Total (N = XX)	Change from the baseline
Screening		
n	XX	
Mean	XX.X	
SD	XX.XX	
Median	XX.X	
Min	XX	
Max	XX	
Day 1		
n	XX	
Mean	XX.X	
SD	XX.XX	
Median	XX.X	
Min	XX	
Max	XX	
Baseline		
n	XX	
Mean	XX.X	
SD	XX.XX	
Median	XX.X	
Min	XX	
Max	XX	
Week 2		
n	XX	XX
Mean	XX.X	XX.X
SD	XX.XX	XX.XX
Median	XX.X	XX.X
Min	XX	XX
Max	XX	XX

ML39355_STATISTICAL ANALYSIS PLAN_Final 2.0_17 June 2020

...

...

...

N: the number of patients in the Treated set (TS).
n: the number of valid measurements.

The baseline value for a variable is defined as the last non-missing value collected before the first study drug administration.
<The following assessments will be presented: Screening, Day 1, Baseline, Week 2, Week 4, Week 8, Week 16, Week 20, Week 26 Day 2, Follow-up visit, Week 39, Week 52>
<The following parameters will be presented: Leukocytes ($10^9/L$), Erythrocytes ($10^{12}/L$), Hemoglobin (g/L), Hematocrit (L/L), Platelets ($10^9/L$), Neutrophils/Leukocytes (%), Eosinophils/Leukocytes (%), Basophils/Leukocytes (%), Monocytes/Leukocytes (%), Lymphocytes/Leukocytes (%).>

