SD	XX.XX	
Median	XX.X	
Min	XX	
Max	XX	
Day 1		
n	XX	
Mean	XX.X	
SD	XX.XX	
Median	XX.X	
Min	XX	
Max	XX	
Baseline		
n	XX	
Mean	XX.X	
SD	XX.XX	
Median	XX.X	
Min	XX	
Max	XX	
Week 4		
n	XX	XX
Mean	XX.X	XX.X
SD	XX.XX	XX.XX
Median	XX.X	XX.X
Min	XX	XX
Max	XX	XX

ML39355_STATISTICAL ANALYSIS PLAN_Final 2.0_17 June 2020

...

...

...

N: the number of patients in the Treated set (TS).
n: the number of valid measurements.

The baseline value for a variable is defined as the last non-missing value collected before the first study drug administration.

Path to the program code, date and time of output

Data extracted: DD.MM.YYYY

<Report all parameters: Heart rate, beats/min/ QT interval, ms/ QTC-F interval, ms>

<The following assessments will be presented: Screening, Day 1, Baseline, Week 4, Week 8, Week 26 Day 2, Week 52>

ML39355_STATISTICAL ANALYSIS PLAN_Final 2.0_17 June 2020

 F. Hoffmann-La Roche Ltd
 ML39355

Table 3.26 ECG. Out of range and General assessment. Frequency table

 Treated set (TS)
 Page X of X

Parameter: XXXXXXXXXXXXXXXXX

	Total (N = XX) n (%)
Screening	
n'	XX
Normal	XX (XX.X)
Abnormal NCS	XX (XX.X)
Abnormal CS	XX (XX.X)
Day 1	
n'	XX
Normal	XX (XX.X)
Abnormal NCS	XX (XX.X)
Abnormal CS	XX (XX.X)
Baseline	
n'	XX
Normal	XX (XX.X)
Abnormal NCS	XX (XX.X)
Abnormal CS	XX (XX.X)
Week4	
n'	XX
Normal	XX (XX.X)
Abnormal NCS	XX (XX.X)
Abnormal CS	XX (XX.X)
...	
...	...

N: the number of patients in the Treated set (TS). n' - the number of valid observations.

n: the number of patients within a specific category. Percentages are based on the corresponding number of valid observations.

ML39355_STATISTICAL ANALYSIS PLAN_Final 2.0_17 June 2020

Path to the program code, date and time of output

Data extracted: DD.MM.YYYY

<Report all parameters: General assessment/ Heart rate, beats/min/ QT interval, ms/ QTC-F interval, ms>

<The following assessments will be presented: Screening, Day 1, Baseline, Week 4, Week 8, Week 26 Day 2, Week 52>

ML39355_STATISTICAL ANALYSIS PLAN_Final 2.0_17 June 2020
Physical examinations

 F. Hoffmann-La Roche Ltd
 ML39355

Table 3.27 Physical examinations. Frequency table

Treated set (TS)

Page X of X

Body system: XXXXXXXXXXXXX

	Total (N = XX) n (%)
Screening	
n'	XX
Normal	XX (XX.X)
Abnormal NCS	XX (XX.X)
Abnormal CS	XX (XX.X)
Day 1	
n'	XX
Normal	XX (XX.X)
Abnormal NCS	XX (XX.X)
Abnormal CS	XX (XX.X)
Baseline	
n'	XX
Normal	XX (XX.X)
Abnormal NCS	XX (XX.X)
Abnormal CS	XX (XX.X)
Week 2	
n'	XX
Normal	XX (XX.X)

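### The laboratory, vital-sign and ECG tables report named visits only: no per-patient worst-value count, no row for unscheduled tests, and no Week 12 row for laboratory and vital-sign values

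*Protocol*

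**What the plan says.** Protocol section 6.5 summarises laboratory, vital-sign and ECG results by measurement time point. For laboratory variables it adds that "shift tables summarizing the frequencies of patients below, within, and above the normal ranges at each time point will be provided". SAP sections 9.4 and 9.5 repeat the by-visit approach, and the shells in SAP section 16.1 fix the rows:

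- **Laboratory (Tables 3.16 to 3.21):** "Baseline, Week 2, Week 4, Week 8, Week 16, Week 20, Week 26 Day 2, Follow-up visit, Week 39, Week 52", with Screening and Day 1 added in the descriptive and out-of-range tables.
- **Vital signs (Tables 3.22 and 3.23):** the same post-baseline visits, with both Week 26 days.
- **ECG (Tables 3.25 and 3.26):** "The following assessments will be presented: Screening, Day 1, Baseline, Week 4, Week 8, Week 26 Day 2, Week 52".

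Protocol section 4.5.13.6 nevertheless schedules vital signs and laboratory tests at Week 12: "Clinical laboratory assessments, including hematology, serum chemistries, and pregnancy test for women of childbearing capacity".

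The protocol also provides for values outside the schedule. Section 4.5.8 says: "The investigator can perform clinical laboratory assessments more frequently, if it is clinically indicated". Section 4.5.9 allows unscheduled ECGs and requires a repeat after a high QTcF, after which "ECG monitoring should continue until QTcF has stabilized on two successive ECGs".

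On stopping drug, Protocol section 3.1 says: "If patients discontinue study treatment early for any reason, they should continue with all scheduled study procedures through Week 26". The tables use the Treated set (any dose received) and set no cut-off relative to the last dose.

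**The concern.** Change in laboratory and ECG parameters is a stated safety endpoint. In a single-arm study of about 60 patients, a reader will want to know how many patients ever had an abnormal value on treatment. Visit rows overlap in patients, so they cannot be added to give that number. A value from an extra test has no row to enter. A patient who has stopped drug still contributes to the Week 16, 20 and 26 rows with nothing to mark the value as off drug.

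The SAP already has a suitable counting rule: section 9.2 counts each patient once per period for AEs. It does not apply that rule to measured values.

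**Working it through.** The documents give no abnormality or discontinuation rates, so every rate below is an assumption used for illustration.

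**1. Denominator.** The only stated figure involved is the sample size: 0.601 × 0.399 × (1.96/0.125)² = 58.96, taken as 60. It reproduces and is not in dispute.

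**2. What the rows can and cannot show.** If a patients are abnormal in each of k rows, the number ever abnormal lies between a (the same patients each time) and a × k (different patients each time). The laboratory shells have k = 6 rows from Week 2 to Week 26. With a = 2:

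- lower bound: 2/60 = 3.3%
- upper bound: 2 × 6 = 12, and 12/60 = 20.0%
- with the missing Week 12 row at the same count: 2 × 7 = 14, and 14/60 = 23.3%

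Identical tables therefore fit very different safety results.

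**3. Per-visit against ever-affected rates.** With an assumed rate p at each of the seven scheduled laboratory visits from Week 2 to Week 26, independent between visits, the ever-affected rate is 1 − (1 − p)⁷:

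| p per visit | ever affected |
|---|---|
| 1% | 6.8% |
| 3% | 19.2% |
| 5% | 30.2% |

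Independence is optimistic for persistent abnormalities; correlation moves the result towards the lower bound in step 2.

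**4. Would windowing absorb unscheduled values?** SAP section 7 defines visit windows but gives no rule that assigns an unscheduled value to a visit or chooses among several values. Even if one were applied, the windows of the six tabulated laboratory visits cover 11 + 11 + 11 + 21 + 21 + 14 = 89 of days 1 to 182 (Week 26 truncated at day 182). All SAP windows together cover 105 of the 182 days.

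**5. What the AE tables already capture.** Protocol sections 5.3.5.4 and 5.3.5.5 make a laboratory or vital-sign abnormality an AE if it has symptoms, changes study treatment, leads to an intervention or another therapy change, or is judged clinically significant. Section 5.2.1 covers ECG deterioration with symptoms or a treatment change. Section 5.3.5.6 covers raised ALT/AST with raised bilirubin or jaundice. SAP section 9.2 counts all of these per patient, whether or not the test was scheduled. What remains is an abnormality meeting none of these criteria. An isolated, asymptomatic ALT/AST rise that changes no therapy and is not judged clinically significant is one example. If found at a scheduled and tabulated visit, it is in that visit's row. If found at an unscheduled test, it is only in Listings 30 to 33.

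**6. Off-drug values.** If the on-drug rate is r, a share d of a row is off drug, and off-drug values are all normal (assumed), the row shows r × (1 − d). With r = 10%, d = 10%, 20% and 30% give 9%, 8% and 7%.

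**The case against.** The strongest reply is that the AE tables do the important work. Anything symptomatic, treatment-changing, needing intervention or, for laboratory and vital signs, judged clinically significant is counted once per patient, up to last dose + 28 days. This stands. A reader might infer from the shells that patients with abnormal values are never counted, or that unscheduled findings reach no table. The documents do not support that.

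Nor do they support the inference that the most extreme values are the ones lost. A QTcF that triggers a repeat is itself in Tables 3.25 and 3.26 when it was found at a scheduled ECG. Under Protocol section 5.1.2, a confirmed increase leads to interruption, which makes it an AE.

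On off-drug values, no shell claims to be on treatment. The Follow-up row is after the last dose by definition, and Weeks 39 and 52 hold only patients continuing pirfenidone. Any mixing is therefore confined to rows through Week 26. A reader might infer a known drift towards normal, but with no discontinuation rate its size cannot be stated.

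Finally, the descriptive tables do deliver change from baseline, and vital signs are not part of that stated endpoint. Both points are fair. They do not answer how many patients were ever abnormal, and AE reporting depends partly on investigator judgement, which per-patient counts of measured values would complement. Protocol section 5.1.1.3 itself names ALT/AST elevation as a reported effect of the drug.

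**Conclusion.** The point holds in a limited form. The measured-value safety tables (3.16 to 3.23, 3.25 and 3.26) cannot give the number of patients with any post-baseline abnormality and have no place for unscheduled values. The laboratory and vital-sign shells drop a scheduled visit. The affected abnormalities are those that do not qualify as AEs: no table counts them per patient, and those from unscheduled tests appear only in listings. The loss of information can be large relative to what the rows show (2 to 12 patients from the same six rows in the illustration), but its actual size depends on rates the documents do not give. The mixing of on-drug and off-drug values through Week 26 follows from the design, and its size is unknown. This is a worthwhile, inexpensive improvement to safety reporting; it does not affect the efficacy analysis.

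**What to change.** Revise the SAP before soft lock, as its section 2 permits:

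1. In Tables 3.18 to 3.21, 3.23 and 3.26, add for each parameter one row for the worst post-baseline value (lowest and highest separately for Low/High shifts), from scheduled and unscheduled tests, counting each patient once in the Treated set.
2. Use the periods in SAP section 9.2: first dose to last dose + 28 days or first rollover dose, with the rollover period shown separately for patients who continue. This window still admits up to 28 days off drug; it is chosen to match the AE tables.
3. Add Week 12 to the laboratory and vital-sign shells.
4. In the visit rows through Week 26, flag values taken after the last dose or show them separately.

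The cost is SAP wording and programming, slightly longer tables and higher reported frequencies. No new visits or tests are needed, provided that unscheduled results are entered in the database. The eCRF is not among the documents, but the SAP says all laboratory, vital-sign and ECG data will be listed, and Listing 2 has a column for the reason for an unscheduled visit.
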